8.2. Protocol Deviations

The number and percentage of subjects with protocol deviations will be summarized, by class of deviations and overall using the FAS as per Protocol Deviations Management Plan (PDMP).

A listing will be prepared containing types of deviations and class along with additional information concerning all protocol deviations as available.

For protocol deviations, only PDs related to the study will be reported. No deviations will be forwarded from the main study.

9. DEMOGRAPHIC AND OTHER BASELINE CHARACTERISTICS

Demographic and other baseline characteristics will be summarized using descriptive statistics for the FAS.

The baseline visits for study ARGX-113-2211 will be conducted after the participant has completed the qualifying study (i.e., week 24 visit ARGX-113-2106). The following demographic and other baseline characteristics will be reported for this study:

- Age (years) - calculated relative to date of consent.
- Age Category (18 - <65 years, 65 - <75 years and \geq 75 years).
- Sex
- Childbearing potential for female subjects only (Yes, No)
 - If No, then reason (Post-Menopausal, Premenarchal, Surgically Sterile, Other)
- Weight (kg)
- Height (cm) [obtained from Argenx – 113-2106]
- BMI (kg/m^2)

Copyright © 2009, 2010, 2012, 2016, 2018, 2019, 2021, 2024 IQVIA. All rights reserved. The contents of this document are confidential and proprietary to IQVIA Holdings Inc. and its subsidiaries. Unauthorized use, disclosure or reproduction is strictly prohibited.

- Anti-Ro/SS-A positive
- Anti-La/SS-B positive
- UWSF- Salivary Flow Rate
- SWSF – Salivary flow Rate
- SGUS
- OSS- Right Eye and Left Eye
- Schirmer- Right Eye and Left Eye
- Schirmer <5mm/5min in at least one eye
- RF
- ESSDAI Total score
- ESSDAI ≥ 10
- clinESSDAI score
 - Is patient a responder (Yes, No)
 - Dosing Regimen (QW, Q2W)
- ESSPRI score
- MFI Score
- SF-36 Score [Physical Component Score (PCS) and Mental Component Score (MCS)]
- Baseline IgG
- 
- 

Summary statistics including n, mean, median, SD, minimum and maximum will be presented for all continuous variables listed above. The number and percentage of subjects will be presented for categorical variables such as sex.

All demographic data and baseline characteristics will be listed as well.

[figure not shown]
9.1. Derivations

- $BMI (kg/m^2) = \text{weight (kg)} / \text{height (m)}^2$

Weight is from Argenx -113-2211 baseline, while height is from Argenx-113-2106

10. PRIOR AND CONCOMITANT THERAPY

All therapies will be coded using WHO-DRUG and presented for the SAF. Anatomical Therapeutic Chemical

confidential and proprietary to IQVIA Holdings Inc. and its subsidiaries. Unauthorized use, disclosure or reproduction is strictly prohibited.

(ATC) selection is performed. ATC coding up to level 4 is available in the clinical database.

Any medication that the participant is receiving at the time of enrollment or receives during the study will be recorded in “Prior and Concomitant Medications” page of the eCRF. The concomitant medications listed in previous study of ARGX-113-2106 which are “Ongoing” will be considered for OLE study.

See [Appendix 3](#) for handling of partial and missing dates for medications.

Based on their start and stop dates, therapies will be allocated to 1 or both of the following categories:

- ‘Prior’ therapies are therapies which strictly started prior to the first dose date of IMP in this study 2211.
- ‘Concomitant’ therapies are therapies which are taken on or after the first dose date of IMP in this study 2211.

If the start and/or stop date is incomplete or missing, the therapy will be allocated to both categories unless the available parts of the start and/or stop date provide evidence that the therapy was not administered during the specific period.

Prior and Concomitant therapies will be tabulated by ATC class (level 1 and 3) and generic term.

Certain medications or treatments are not permitted during the periods listed in [Table 4](#) of protocol.

All prior and concomitant therapies will be listed.

11. STUDY MEDICATION EXPOSURE

Exposure to IMP in days will be summarized for the SAF.

The infusion start date/time and infusion end date/time of each dose administered along with total dose administered at each visit will be recorded. The date of first study infusion will be taken from the eCRF “Exposure - Infusion” form. The date of last study infusion will be taken from the eCRF “End of Treatment” form. Interruptions, temporary discontinuation, compliance, and dose changes are not considered for duration of exposure.

Table D: Treatment Administered Duration and the number of Administered doses.

The treatment exposure into different dosing regimen are described in the below table:

Classification based Dosing	Regime pattern
-----------------------------	----------------

[figure not shown]

Participants continuing QW (QW)	Start : QW During the study : QW End of study at week 48 : QW
Participants switching to and continuing Q2W (Q2W)	Start : Q2W During the study : Q2W End of study at week 48 : Q2W
Participants switching to Q2W at start of OLE and switching to QW (SQW)	Start : Day 1- Q2W During the study : The participant becomes a non-responder at week 16, 24, 32, 36, 40, 44, or an unscheduled visit where which a clinESSDAI result has resulted a non-responder outcome End of study at Week 48 : QW
Participants continuing QW and switching to Q2W later during OLE (SQ2W)	Starts: Day 1 – QW During the study: the study the participant becomes a responder at week 16, 24, 32, 36, 40, 44, or an unscheduled visit where which a clinESSDAI result has resulted a responder outcome -Q2W End of study at week 48 : Q2W

The above definitions do not consider authorized temporary discontinuation of treatment. Note the disease worsening is only recorded on the ECRF on weeks 24, 32, 40 and 44 or unscheduled. For more accurate interpretation of the regimen the actual imp allocation must be considered. Where a scheduled imp allocation has not occurred due to procedure or a missed visit, it will be considered as being undertaken for the purpose of checking the regimen period. Note: further detail may be required depending on the data received and this will be detailed within the ADAM Specifications.

Treatment Administration Duration will be defined overall from Start Day 1 to end of treatment or end of study.

As per protocol, a variation of more than 10% of the amount of 10 mg/kg will be considered an overdose. Overdose information is as collected in “Exposure – Infusion” page of eCRF.

Copyright © 2009, 2010, 2012, 2016, 2018, 2019, 2021, 2024 IQVIA. All rights reserved. The contents of this document are confidential and proprietary to IQVIA Holdings Inc. and its subsidiaries. Unauthorized use, disclosure or reproduction is strictly prohibited.

The number of administrations of IMP per participant and the compliance will be summarized descriptively overall, summing the different doses from the different regimens. The total treatment administration duration will be summarized using descriptive statistics. All IMP administration data will be listed. Participants with an overdose of IMP will be listed.

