6.6. Dose Modification

The maximum total efgartigimod dose per efgartigimod infusion is 1200 mg for participants weighing ≥ 120 kg. The IMP weight-based dose will be recalculated if a participant's weight has changed (increased or decreased) by more than 10% from OLE baseline (ie, weight prior to IMP infusion on day 1 of the ARGX-113-2211 study).

Modifications to the schedule of dosing are permitted as described in Section 4.1.

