6.8. Treatment of Overdose

Any dose of efgartigimod greater than the intended QW or Q2W amount will be considered an overdose.

The sponsor does not recommend specific treatment for an overdose.

In the event of an overdose, the investigator or treating physician will:

- Evaluate the participant to determine if IMP will be interrupted
- Closely monitor the participant for any AE/SAE and laboratory abnormalities (as medically appropriate and at least until the next scheduled follow-up)
- Record the overdose in the eCRF and the quantity of the excess dose as well as the duration of the overdose

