10.3.1. Definition of AE

AE Definition

• An AE is any untoward medical occurrence in a clinical study participant, temporally associated with the use of IMP, whether or not considered related to the IMP• NOTE: An AE can therefore be any unfavorable and unintended sign (including an abnormal laboratory finding), symptom, or disease (new or exacerbated) temporally associated with the use of IMP

Events to be Collected as AEs

• Any abnormal laboratory test results (hematology, clinical chemistry, or urinalysis) or other safety assessments (eg, ECG, radiological scans, vital sign measurements), including those that worsen from baseline, considered clinically significant in the medical and scientific judgment of the investigator (ie, not related to progression of underlying disease)• Exacerbation of a chronic or intermittent pre-existing condition including either an increase in frequency and/or intensity of the condition• New condition detected or diagnosed after IMP administration even though it could have been present before the start of the study• Signs, symptoms, or the clinical sequelae of a suspected intervention-intervention interaction• Signs, symptoms, or the clinical sequelae of a suspected overdose of either IMP or a concomitant medication. Overdose per se will not be reported as an AE/SAE unless it is an intentional overdose taken with possible suicidal/self-harming intent. Such overdoses will be reported regardless of sequelae• Lack of efficacy or failure of expected pharmacological action per se will not be reported as an AE or SAE. Such instances will be captured in the efficacy assessments. However, the signs, symptoms, and/or clinical sequelae resulting from lack of efficacy will be reported as AE or SAE if they fulfill the definition of an AE or SAE

Events NOT to be Collected as AEs

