3.4. Changes to Analysis from Protocol

The Biomarker data will not be analyzed due to the lack of available data to BIOS.

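### SAP 11 credits the protocol with a 10% overdose threshold, but protocol 6.8 sets no tolerance and SAP 3.4 declares no departure on overdose

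*SAP*

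**What the plan says.** SAP 11 (Study Medication Exposure) gives the definition: "As per protocol, a variation of more than 10% of the amount of 10 mg/kg will be considered an overdose". The next sentence opens "Overdose information is as collected in" and names the Exposure – Infusion page of the eCRF. The section then promises two listings, one of all IMP administration data and one of participants with an overdose. SAP 11.1 (Derivations) contains no overdose derivation.

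Protocol 6.8 (Treatment of Overdose) reads: "Any dose of efgartigimod greater than the intended QW or Q2W amount will be considered an overdose". It instructs the investigator: "Record the overdose in the eCRF and the quantity of the excess dose".

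The 10% figure in the protocol's dosing text belongs to a different rule. Under protocol 6.6 (Dose Modification), repeated in footnote m of the Schedule of Activities, the weight-based dose is recalculated when body weight has changed "by more than 10% from OLE baseline". Section 6.6 also sets the cap: "The maximum total efgartigimod dose per efgartigimod infusion is 1200 mg for participants weighing ≥ 120 kg".

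SAP 3.4 (Changes to Analysis from Protocol) consists of one statement: "The Biomarker data will not be analyzed due to the lack of available data to BIOS".

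**The concern.** The SAP names the protocol as its source for a threshold that the supplied protocol does not contain. The two definitions differ in three ways:

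- **Tolerance:** the SAP allows 10%; the protocol allows none.
- **Direction:** the SAP speaks of a variation, which literally runs both ways; the protocol counts only excess.
- **Reference dose:** the SAP measures against 10 mg/kg without mentioning the 1200 mg maximum.

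A programmer who follows the SAP sentence would build an overdose listing that does not match the protocol. A reader of the study report would be told that the listing follows the protocol definition. Safety is the primary objective, so the classification should be right even where the output is a single listing.

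**Working it through.** The plan has no figure to reproduce here. The check is a comparison of the two definitions, followed by arithmetic on what each one would flag.

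**Inputs**

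- Dose 10 mg/kg, maximum 1200 mg per infusion (protocol 6.6).
- Protocol threshold: any dose above the intended dose (protocol 6.8).
- SAP threshold: more than 10% variation from 10 mg/kg (SAP 11).
- Body weight *w*: assumed. The documents give no weight distribution. Enrolment is up to about 30 (protocol 9.5).

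**Formulas**

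- Intended dose = min(10 × *w*, 1200) mg.
- SAP upper limit, taken as written without the cap = 1.10 × 10 × *w* = 11 × *w* mg.
- SAP lower limit, if the variation is two-sided = 0.90 × 10 × *w* = 9 × *w* mg.
- Gap = SAP upper limit − intended dose. Doses in this range are overdoses under the protocol but not under the SAP.

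**Excesses that the SAP rule would leave off**

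| Assumed weight | Intended dose | SAP upper limit | Gap | Gap as % of intended |
|---|---|---|---|---|
| 50 kg | 500 mg | 550 mg | 50 mg | 10% |
| 70 kg | 700 mg | 770 mg | 70 mg | 10% |
| 110 kg | 1100 mg | 1210 mg | 110 mg | 10% |
| 120 kg | 1200 mg | 1320 mg | 120 mg | 10% |
| 130 kg | 1200 mg | 1430 mg | 230 mg | 230/1200 = 19.2% |

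Above 120 kg the relative gap is 11 × *w*/1200 − 1 and grows with weight. If the cap is read into the SAP rule, the limit stays at 1.10 × 1200 = 1320 mg and the gap stays at 10%.

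**Doses that the SAP rule would wrongly flag, if it is read as two-sided**

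- At 70 kg, any dose below 9 × 70 = 630 mg would be called an overdose, although it is an underdose.
- If the cap is ignored, a correct 1200 mg dose falls below 9 mg/kg once *w* exceeds 1200/9 = 133.3 kg, and would be flagged.

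**If the eCRF record decides the listing**

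The gap is 0 mg and nobody is misclassified. The SAP's definition then does not describe what is listed.

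**The case against.** The strongest reply is that the SAP sentence may have no effect. The sentence after it points to overdose information collected on the eCRF, protocol 6.8 has the investigator record overdoses there under its own zero-tolerance definition, and SAP 11.1 derives nothing. On that reading the listing simply shows what sites recorded. This is the more natural reading, and it stands as a limit on the consequence. It does not rescue the sentence, which is still a false statement of the protocol's definition. Nor does the SAP say outright which source governs.

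A reader might infer that overdoses will be lost from the safety results, with adverse event reporting offering no protection. The documents do not support that. Protocol 10.3.1 does say "Overdose per se will not be reported as an AE/SAE unless it is an intentional overdose taken with possible suicidal/self-harming intent", but the same bullet has signs, symptoms and clinical sequelae of a suspected overdose collected as adverse events. Only a symptom-free excess falls outside, and its dose still appears in the listing of all administrations. What is at risk is how a dose is classified, not whether it can be seen.

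It can also be said that a tolerance is sensible to absorb rounding. That may be so, but it would then be the SAP's own rule, and it should be labelled as such.

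The objection that SAP 3.4 concerns changes to analysis, while protocol 6.8 concerns treatment management, has some force: protocol section 9 plans no overdose analysis. The missing entry in 3.4 is therefore secondary. The main fault is the attribution to the protocol.

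Finally, SAP 1 cites protocol V1.0 dated 24FEB2023, and the title page of the supplied protocol is not available, so the match cannot be confirmed. Nothing in the supplied text supports a 10% overdose rule.

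**Conclusion.** The point holds and is minor. Judged against the supplied protocol, the definition in SAP 11 is misattributed, and it differs from protocol 6.8 in tolerance, in literal direction and in its silence on the cap.

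The effect depends on which source drives the listing. If the SAP rule is applied, excesses of up to 10% of the intended dose are left off, and more than 10% above 120 kg if the cap is ignored. A two-sided reading adds false flags. If the eCRF record governs, there is no misclassification, only a wrong definition in print. The milligram figures rest on assumed weights, and it is possible that no participant is affected under either reading.

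The reach is one descriptive safety listing. No primary or secondary endpoint, summary estimate or inference changes. It is tempting to suppose that the 10% was carried over from the weight-change rule in protocol 6.6, but the documents do not say so.

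**What to change.** Replace the sentence in SAP 11 with:

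> Per protocol 6.8, an overdose is any administered dose that exceeds the intended dose (10 mg/kg on the weight used for dosing under protocol 6.6, maximum 1200 mg). The overdose listing will present all overdoses recorded on the Exposure – Infusion eCRF page, plus any administration whose recorded dose exceeds the intended dose.

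This restores the protocol definition, brings in the cap, and settles what happens when the site record and the recorded dose disagree: either one is enough for listing.

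If a rounding tolerance is wanted, apply it upward only against the capped intended dose, remove the attribution to the protocol, and declare it in SAP 3.4.

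The cost is one replaced SAP statement and a simple comparison of recorded with intended dose in programming, plus one line in SAP 3.4 if a tolerance is kept. The eCRF and data collection do not change.

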11.1. Derivations

- Total treatment administration duration (days) = date of last IMP administration – date of first IMP administration + 1.
- Number of administrations = Number and percentage of participants receiving 1, 2, 3 etc. administrations overall.

12. STUDY MEDICATION COMPLIANCE

The infusion is given once a week by site staff or delegate. At least, the first 3 doses of IMP (for QW dosing regimen: baseline visit and the week 1 and 2 visits; for Q2W dosing regimen: baseline visit and the week 2 and 4 visits; or subsequent if previous doses are missed) must be administered on-site.

Compliance will be calculated for Q2W participants who continued Q2W dosing regimen throughout the study. The dosing regimen of other participants will be listed in the listing.

The compliance will be descriptively summarized for the same subset. Compliance will be further categorized as <80, 80-100, >100.

12.1. Derivations

Compliance is defined as: $100 * (\text{number of doses received} / \text{number of doses expected})$.

Number of doses expected will be based on participants expecting study drug infusion/administration on eCRF page “Exposure – Infusion” irrespective of dosing received.

Only visits up to treatment discontinuation are considered in the compliance calculation.

13. EFFICACY OUTCOMES

13.1. Efficacy Endpoints

The efficacy analyses will be performed for the FAS and will be analyzed on data observed.

Copyright © 2009, 2010, 2012, 2016, 2018, 2019, 2021, 2024 IQVIA. All rights reserved. The contents of this document are confidential and proprietary to IQVIA Holdings Inc. and its subsidiaries. Unauthorized use, disclosure or reproduction is strictly prohibited.

13.1.1. Proportion of CRESS Responders on ≥ 3 of 5 items at Week 24 and 48

The CRESS composite measures below mentioned assessments which are developed to assess treatment efficacy in participants with pSS:

- 1) Systemic disease activity: clinESSDAI
- 2) Patient-reported symptoms: ESSPRI
- 3) Tear gland function: Schirmer’s test and OSS.
- 4) Salivary gland function: UWSF rate and SGUS
- 5) Serology (serum IgG and/or RF)

The efficacy endpoint is the proportion of responders on ≥ 3 non-missing of 5 items at week 24 and 48 using CRESS.

CRESS consists of the following items, with definitions of treatment response and lower disease activity:

1) Systemic disease activity: This will be measured with clinESSDAI (Seror [a], et al., 2016)⁸.

The clinESSDAI consists of 11 domains, related to organ involvement (cutaneous, pulmonary, renal, articular, muscular, peripheral nervous system, central nervous system, hematological, glandular, constitutional, and lymphadenopathic). The ClinESSDAI includes all ESSDAI domains except the biological domain.

Table E: Domain Weights of ClinESSDAI

Domain (activity level)	ClinESSDAI Weights
Constitutional (0-2)	4
Lymphadenopathy (0-3)	4
Glandular (0-2)	2
Articular (0-3)	3
Cutaneous (0-3)	3
Pulmonary (0-3)	6
Renal (0-3)	6
Muscular (0-3)	7
Peripheral nervous system (0-3)	5
Central nervous system (0-3) ^{Seror 2015}	5
Hematological (0-3)	2
Biological (0-2)	NA*

Copyright © 2009, 2010, 2012, 2016, 2018, 2019, 2021, 2024 IQVIA. All rights reserved. The contents of this document are confidential and proprietary to IQVIA Holdings Inc. and its subsidiaries. Unauthorized use, disclosure or reproduction is strictly prohibited.

Domain (activity level)	ClinESSDAI Weights
Score total	0-135

*NA: Not Applicable

The activity levels of each domain (range: 0-3 points or 2 points) are multiplied by their respective weights (range: 1-7 points) to obtain the total score. The final score, the sum of all domain scores, falls between 0 (no disease activity) and 135. For CNS, score values indicates (0= None, 2=Moderate and 3= High). If a domain score is missing, final score will not be calculated.

These 11 components are present in database and these components gradings are multiplied by their weights as mentioned in table above at database level. The values for each domain are obtained from CRF and then the Total Score consisting of 11 components is available at database level and hence, no score derivation is required.

Responder with low disease activity (clinESSDAI score of < 5 points) is obtained at week 24 and 48⁴.

2) Patient-reported symptoms: This will be measured with ESSPRI.

ESSPRI is a questionnaire that has been developed to measure self-reported symptoms in participants with pSS.

The ESSPRI has 3 items that measure dryness, fatigue, and pain over a recall period of “the last 2 weeks.” Each item includes a numeric rating scale ranging from 0 “No symptoms (dryness, fatigue or pain)” to 10 “Maximal imaginable (dryness, fatigue or pain).” These individual 3 item scores are obtained from electronic clinical outcome assessment (eCOA).

The ESSPRI Total score is derived by summation of all the three numeric scores and then averaging the same. If any of the three numeric scores are missing, the total score will be missing.

The ESSPRI total score ranges from 0 to 10, with higher scores indicating more symptoms.

Higher score in ESSPRI reflects more severe symptomatology.

[figure not shown]
Clinically meaningful response is defined as a decrease of ≥ 1 point or $\geq 15\%$ from baseline.

3) Tear gland function: This will be measured with Schirmer’s test and OSS.

The Schirmer’s test measures total tear secretion is used to identify aqueous-deficient dry eye, the type of dry eye primarily associated with Sjögren’s syndrome. In the absence of anesthesia, the Schirmer test measures reflex tearing, while the test performed with anesthesia measures basal tear secretion.

Schirmer’s test is an assessment of tear gland function in which a strip of filter paper is applied under the eyelid to measure the quantity of tear production. A result of ≤ 5 mm indicates abnormal tear gland function. OSS will be used in this study to assess tear gland function in participants with pSS. OSS uses lissamine green dye to grade the conjunctiva, and fluorescent dye to grade the cornea.

- If Schirmer’s test is ≤ 5 mm at baseline (abnormal), a response is defined as an increase of at least 5 mm from baseline. OR

Copyright © 2009, 2010, 2012, 2016, 2018, 2019, 2021, 2024 IQVIA. All rights reserved. The contents of this document are confidential and proprietary to IQVIA Holdings Inc. and its subsidiaries. Unauthorized use, disclosure or reproduction is strictly prohibited.

- If OSS is ≥ 3 points at baseline (abnormal), a response is defined as a decrease of at least 2 points from baseline OR
- If both OSS and Schirmer’s scores are normal at baseline, a response is defined as no change that results in an abnormal OSS or Schirmer’s score, to be presented as stable.
- For the tear gland analysis, (Schirmer’s test, OSS) mean scores of both eyes are used.

Here, the mean value calculated for both the eyes at each visit will be considered and CRESS response will be derived.

These values for Schirmer’s test and OSS are obtained from eCRF data.

4) Salivary gland function: This will be measured with UWSF and SGUS.

The following parameters and grades are considered for measure of SGUS parameter:

- (1) Parenchymal echogenicity compared to thyroid parenchyma, graded 0–1
- (2) homogeneity, graded 0–3
- (3) presence of hypoechoic areas in parenchyma, graded 0–3
- (4) presence of hyperechoic foci, graded 0–3 in parotid glands and 0–1 in submandibular glands
- (5) clearness of the salivary gland border, graded 0–3

Table F: Salivary gland Function grades

Salivary Gland Type			
Parotid (left)	Parotid (right)	Submandibular (left)	Submandibular (right)
Parenchymal echogenicity compared to thyroid parenchyma, graded 0–1	Parenchymal echogenicity compared to thyroid parenchyma, graded 0–1	Parenchymal echogenicity compared to thyroid parenchyma, graded 0–1	Parenchymal echogenicity compared to thyroid parenchyma, graded 0–1
homogeneity, graded 0–3	homogeneity, graded 0–3	homogeneity, graded 0–3	homogeneity, graded 0–3
presence of hypoechoic areas in parenchyma, graded 0–3	presence of hypoechoic areas in parenchyma, graded 0–3	presence of hypoechoic areas in parenchyma, graded 0–3	presence of hypoechoic areas in parenchyma, graded 0–3
presence of hyperechoic foci, graded 0–3 in parotid glands	presence of hyperechoic foci, graded 0–3 in parotid glands	presence of hyperechoic foci, graded 0–1 in submandibular glands	presence of hyperechoic foci, graded 0–1 in submandibular glands

Copyright © 2009, 2010, 2012, 2016, 2018, 2019, 2021, 2024 IQVIA. All rights reserved. The contents of this document are confidential and proprietary to IQVIA Holdings Inc. and its subsidiaries. Unauthorized use, disclosure or reproduction is strictly prohibited.

clearness of the salivary gland border, graded 0–3	clearness of the salivary gland border, graded 0–3	clearness of the salivary gland border, graded 0–3	clearness of the salivary gland border, graded 0–3
Score Range – 0 to 13	Score Range – 0 to 13	Score Range – 0 to 11	Score Range – 0 to 11

The overall ultrasound score is calculated by summation of the grades for the 5 above mentioned parameters - for all 4 major salivary glands. The overall ultrasound score can range from 0 to 48.

If any parameter is not assessed, the whole score cannot be derived, no substitutes for missing data.

Responder for salivary gland function has two components:

- UWSF: at least 25% increase in score, or if score is 0 mL/min at baseline, any increase from baseline OR
- SGUS: at least 25% decrease in total Hocevar score³ from baseline

Unstimulated whole salivary flow (UWSF) will be measured as ml per minute.

5) Serology: It is measured with serum IgG and RF

For the biological domain, levels of rheumatoid factor (RF), and IgG are measured based on blood sample examined in the laboratory. The amount of RF antibody will be measured in - (IU/ml) [(IU/ml)] and IgG will be assessed in (g/L).

A responder for biological domain is defined as follows:

- A response is defined as $\geq 10\%$ reduction in IgG from baseline or
- A response is defined as $\geq 25\%$ decrease in rheumatoid factor (RF) from baseline.

The proportion of participants with CRESS responders on ≥ 3 of 5 items at week 24 and 48 will be provided along with exact 90% CIs.

13.1.2. Proportion of Participants with Minimal Clinically Important Improvement in ESSDAI: Improvement of ≥ 3 Points in ESSDAI Score at Week 24 and 48 & Proportion of Participants with Low Disease Activity: ESSDAI Score of < 5 at Week 24 and 48

As explained in Section 14.2.1.1, the ESSDAI (Seror [a], et al., 2015)⁹ consists of 12 domains, 11 related to organ involvement (cutaneous, pulmonary, renal, articular, muscular, peripheral nervous system, central nervous system, hematological, glandular, constitutional, and lymphadenopathic) and 1 biological domain reflecting B-cell activity.

Table G: Domain Weights of ESSDAI

Domain (activity level)	ESSDAI Weights
Constitutional (0-2)	3

Copyright © 2009, 2010, 2012, 2016, 2018, 2019, 2021, 2024 IQVIA. All rights reserved. The contents of this document are confidential and proprietary to IQVIA Holdings Inc. and its subsidiaries. Unauthorized use, disclosure or reproduction is strictly prohibited.

Domain (activity level)	ESSDAI Weights
Lymphadenopathy (0-3)	4
Glandular (0-2)	2
Articular (0-3)	2
Cutaneous (0-3)	3
Pulmonary (0-3)	5
Renal (0-3)	5
Muscular (0-3)	6
Peripheral nervous system (0-3)	5
Central nervous system (0-3)	5
Hematological (0-3)	2
Biological (0-2)	1
Score total	0-123

[figure not shown]
Each domain is scored on a range of values depending on their activity level, which can include 3 or 4 levels, into a scale from 0: No, 1: Low, 2: Moderate, 3: High.

For ESSDAI, the activity levels of each domain (range: 0-3 points or 0-2 points) are multiplied by their respective weights (range: 1-6 points) to obtain the total score. The final score, the sum of all domain scores, falls between 0 (no disease activity) and, theoretically, 123 (higher disease activity). ESSDAI cannot be assessed if any domain is missing.

The Biological domain for post baseline visits will be derived using following variables at analysis level:

Biological [1]	No=0	Absence of any of the following biological features
	Low=1	Clonal component and/or hypocomplementemia (low C4 or C3 or CH50) and/or hypergammaglobulinemia or high IgG level between 16 and 20 g/L
	Moderate=2	Presence of cryoglobulinemia and/or hypergammaglobulinemia or high IgG level > 20 g/L, and/or recent onset hypogammaglobulinemia or recent decrease of IgG level (< 5 g/L)

The proportion of participants with improvement of ≥ 3 points in score and the proportion of participants having ESSDAI score of < 5 at week 24 will be provided, along with exact 90% CIs and for each of these two endpoints.

Copyright © 2009, 2010, 2012, 2016, 2018, 2019, 2021, 2024 IQVIA. All rights reserved. The contents of this document are confidential and proprietary to IQVIA Holdings Inc. and its subsidiaries. Unauthorized use, disclosure or reproduction is strictly prohibited.

13.1.3. Proportion of Participants with Minimal Clinically Important Improvement in clinESSDAI: Improvement of ≥ 3 Points in clinESSDAI Score at Week 24 and 48 & Proportion of Participants with Low Disease Activity: clinESSDAI score of < 5 at Week 24 and 48

As explained in Section 14.2.1.1 of SAP, the ClinESSDAI includes all ESSDAI domains except the biological domain.

The proportion of participants with improvement of ≥ 3 points in clinESSDAI score and the proportion of participants having clinESSDAI score of < 5 at week 24 and 48 will be provided, along with exact 90% CIs and for each of these two endpoints.

13.1.4. Proportion of Participants with Minimal Clinically Important Improvement in ESSPRI: Decrease of 1 Point or $\geq 15\%$ at Week 24 and 48

The Information on the derivation of ESSPRI total score is provided in Section 14.2.1.1.

The proportion of participants with decrease of 1 point or $\geq 15\%$ in ESSPRI total score at week 24 and 48 will be provided and along with exact 90% CIs for each of these two endpoints.

13.1.5. Change in ESSDAI Score, clinESSDAI Score and ESSPRI Score at Week 24 and 48

These scores will be descriptively summarized for actual scores and changes from baseline in ESSDAI, clinESSDAI, and ESSPRI at scheduled timepoint of week 16, 24, 36 and 48. In addition, the same analysis in clinESSDAI and ESSDAI will be assessed for three subgroups (mutually exclusive) based on the dosing regimen defined below.

- For patients continuing QW: the population that patients continuing QW is defined as those continue QW throughout the study.
- For patients switching to Q2W: the population that patients switching to Q2W is defined as that switch from QW to Q2W at any timepoint.
- For patients switching back to QW from Q2W: the population that patients switching back to QW from Q2W is defined as those switches from Q2W to QW at any timepoint.

Plots of mean changes from the OLE baseline will be presented along with their 90% confidence intervals at each scheduled timepoint of week 16, 24, 36 and 48 for ESSDAI, clinESSDAI, and ESSPRI. Box and Whisker plots will also be presented for the change from OLE baseline for each scheduled timepoint.

Copyright © 2009, 2010, 2012, 2016, 2018, 2019, 2021, 2024 IQVIA. All rights reserved. The contents of this document are confidential and proprietary to IQVIA Holdings Inc. and its subsidiaries. Unauthorized use, disclosure or reproduction is strictly prohibited.

13.1.6. Proportion of Participants with STAR Score of ≥ 5 at Week 24 and 48

STAR has been developed to assess the efficacy of treatments for pSS.

The details of each of the components remains the same as explained in Section 14.2.1.1. This composite measure contains 5 domains (like CRESS):

- Systemic activity: If participant has clinESSDAI score decreased by ≥ 3 points at week 24 and 48, in that case the participant will be scored with 3 points.
- Patient-reported outcome: If participant has ESSPRI score decrease of at least 1 point or $\geq 15\%$ at week 24 and 48, in that case the participant will be scored with 3 points.
- Lacrimal gland function (assessed by Schirmer's test or OSS)

Here there are two criteria associated w.r.t Schirmer's test:

- If Schirmer's test is ≤ 5 mm at baseline (abnormal) in at least 1 eye, a response is defined as an increase of at least 5 mm from baseline.
- If Schirmer's scores are normal in both eyes at baseline, a response is defined as no change to abnormal.

Also, there are two criteria associated w.r.t OSS:

- If OSS score ≥ 3 points at baseline (abnormal) in at least 1 eye, a response is defined as a decrease of at least 2 points from baseline.
- If OSS scores are normal in both eyes at baseline, a response is defined as no change to abnormal.

If either of the Schirmer's test or OSS assessment criteria are met, 1 point is assigned.

- Salivary gland function

Here there are two criteria associated w.r.t UWSF:

- If score > 0 at baseline: increase of $\geq 25\%$ from baseline.
- If score is 0 at baseline: any increase in UWSF from baseline.

OR

SGUS: $\geq 25\%$ decrease in total Hocevar score from baseline

[figure not shown]
[figure not shown]
If either of the UWSF or SGUS assessment criteria are met, 1 point is assigned.

- Biological (assessed by IgG or RF): 1 point is assigned if,
 - IgG: $\geq 10\%$ reduction
 - RF: $\geq 25\%$ decrease

The proportion of participants with STAR score of ≥ 5 points at week 16, 24, 36 and 48 will be provided and along

with exact 90% CIs.

Copyright © 2009, 2010, 2012, 2016, 2018, 2019, 2021, 2024 IQVIA. All rights reserved. The contents of this document are confidential and proprietary to IQVIA Holdings Inc. and its subsidiaries. Unauthorized use, disclosure or reproduction is strictly prohibited.

13.2. [REDACTED]

[REDACTED]

13.2.5 [REDACTED]

[REDACTED]

[REDACTED]

[REDACTED]

Copyright © 2009, 2010, 2012, 2016, 2018, 2019, 2021, 2024 IQVIA. All rights reserved. The contents of this document are confidential and proprietary to IQVIA Holdings Inc. and its subsidiaries. Unauthorized use, disclosure or reproduction is strictly prohibited.

[Redacted]

13.2.7

[Redacted]

[Redacted]

13.2.8.

[Redacted]

[Redacted]

[Redacted]

Copyright © 2009, 2010, 2012, 2016, 2018, 2019, 2021, 2024 IQVIA. All rights reserved. The contents of this document are confidential and proprietary to IQVIA Holdings Inc. and its subsidiaries. Unauthorized use, disclosure or reproduction is strictly prohibited.

[Redacted]

13.2.9.

[Redacted]

[Redacted]

13.2.10.

[Redacted]

[Redacted]

13.2.11.

[Redacted]

[Redacted]

[Redacted]

Copyright © 2009, 2010, 2012, 2016, 2018, 2019, 2021, 2024 IQVIA. All rights reserved. The contents of this document are confidential and proprietary to IQVIA Holdings Inc. and its subsidiaries. Unauthorized use, disclosure or reproduction is strictly prohibited.

13.2.12.

[Redacted]

[Redacted]

13.2.13.

[Redacted]

13.2.14.

[Redacted]

[Redacted]

[Redacted]

Copyright © 2009, 2010, 2012, 2016, 2018, 2019, 2021, 2024 IQVIA. All rights reserved. The contents of this document are confidential and proprietary to IQVIA Holdings Inc. and its subsidiaries. Unauthorized use, disclosure or reproduction is strictly prohibited.

[Redacted]

[Redacted]

13.3

[Redacted]

[Redacted]

13.3

[Redacted]

[Redacted]

13.3

[Redacted]

[Redacted]

13.3.

[Redacted]

[Redacted]

[Redacted]

Copyright © 2009, 2010, 2012, 2016, 2018, 2019, 2021, 2024 IQVIA. All rights reserved. The contents of this document are confidential and proprietary to IQVIA Holdings Inc. and its subsidiaries. Unauthorized use, disclosure or reproduction is strictly prohibited.

13.3.5

